11.1.3 Secondary Analyses

We will use the Wilcoxon Rank Sum test for not normally distributed data and Fisher's exact test for categorical data to compare changes between the two groups. All tests will be two tailed; $p < 0.05$ will be defined as significant. Data will be analyzed using STATA, Graph Pad Prism and IBM SPSS.

The parameters assessed via blood sampling during and after the bicycle exercise will be analyzed using descriptive statistics and appropriate graphical representation.

Values of pH, base excess and bicarbonate at 120 minutes after beginning of the bicycle exercise will be compared to the baseline values using medians and interquartile range as well as appropriate graphical representation. The statistical significance of the difference between the two medians will be tested using the Wilcoxon signed-rank test for paired data.

The same statistical procedure will be applied to the values of blood glucose at the end of, as well as 60 and 120 minutes after beginning of the bicycle intervention.

Safety outcomes (please refer to chapter 5.2) will be illustrated using descriptive statistics.

Re-hospitalization and unplanned re-consultation rate 3 months after study enrollment will be quantified by number of hospitalizations and/or physician re-consultations as well as total length of hospitalization(s) in days. Data will be tested using the Mann-Whitney U-test.

SIMPAQ questionnaire results will be depicted using descriptive statistics and medians of the two groups evaluated using the Mann-Whitney U-test.

Results of the actigraph readouts at baseline, 3 months and 6 months will be compared inter-individually to assess if the endpoint has been fulfilled or not.

Number of anti-diabetic medication at 1, 2, 3 and 6 months as well as one year compared to baseline will be depicted using Graph Pad Prism. Average number of medication in both groups will be compared at 3 and 6 months after baseline.

Health-care related costs will be calculated for each study arm based on actual costs in respective cantons for medication as well as according to Tarmed (outpatient-clinic tariff system).

SF-36 questionnaire will be evaluated using IBM SPSS and compared between the two groups using the Mann-Whitney U-test at baseline and after 6 months.

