4.3 Secondary Objectives

Secondary objectives are

- To implement methods to monitor patients' activity levels and support motivation for the following training sessions
- To test the impact of an intensive lifestyle intervention on HbA1c-levels and its dependency on the level at baseline
- To assess change of weight at 3, 6 and 12 months after enrollment compared to baseline and to standard of care
- To evaluate changes in heart rate, blood pressure, blood glucose, pH, base excess and bicarbonate after a 30-minute bicycle exercise
- To evaluate re-hospitalization and unplanned re-consultation rate during the study in both arms
- To evaluate changes in physical activity during and after the study intervention compared to baseline
- To evaluate number of anti-diabetic medication at 30, 60, 90 days, as well as 6 months and one year compared to baseline in both arms
- Cost-effectiveness
- To compare changes in quality of life in the intervention group to the standard-of-care group.

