5.2 Secondary Outcomes

Secondary outcomes are as follows:

- Absolute HbA1c reduction per stratification group (groups consist of HbA1c > 14 %, HbA1c < 14 % and > 10 % and HbA1c < 10 %)
- Change of HbA1c at 6 and 12 months after enrollment compared to control group
- Proportion of patients achieving target per stratified group after 3 and 6 months without anti-diabetic medication other than Metformin
- Changes in pH, base excess and bicarbonate 90 minutes after bicycle exercise compared to baseline
- Change of weight at 3, 6 and 12 months after enrollment compared to baseline and to standard of care
- Changes in blood glucose at the end of, as well as 30 and 90 minutes after bicycle exercise compared to baseline
- Feasibility of bicycle exercise at study enrollment in the ER, defined as absence of problem reports through the study team (e.g. patient cooperation)
- Safety of bicycle exercise, defined as:
 - o Absence of SAEs during the exercise
 - o No signs of acute cardiopulmonary decompensation in the patient during bicycle exercise
 - o No necessity to prematurely terminate the bicycle intervention because of other health or safety concerns
- Safety of intensive lifestyle intervention within 3 months following study enrollment, with the following endpoints:
 - o Number of SAEs in the intervention group compared to the control group
 - o Number of rescue medication administered in the intervention group compared to the control group
- Length of initial hospitalization, as well as number and length of re-hospitalizations and unplanned re-consultations within 3 months after initial consultation
- Changes in physical activity at 6 months compared to baseline assessed by SIMPAQ questionnaire (Endpoint: hours of physical activity)
- Changes in physical activity at 3 and 6 months compared to baseline assessed by actigraph (Endpoint: Stepgoal reached)
- Number of anti-diabetic medication at 30, 60, 90 days, as well as 6 months and one year compared to baseline in both arms
- Proportion of patients receiving insulin therapy after 6 months and one year in the intervention group compared to the control group
- Absolute health-care related costs at 3, 6 and 12 months in both arms
- Quality of life at 6 months in the intervention group compared to standard of care as assessed by SF-36 questionnaire.

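### Continuous secondary outcomes are tested without baseline adjustment, which is valid but costs precision; the SF-36 test at baseline is uninformative, and level versus change is unsettled for SF-36 and SIMPAQ

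*Protocol*

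**What the plan says.** Protocol Section 11.1.3 opens with a general rule: "We will use the Wilcoxon Rank Sum test for not normally distributed data and Fisher's exact test for categorical data to compare changes between the" (the quotation stops just before the sentence names the arms). Section 5.2 defines HbA1c ("Change of HbA1c at 6 and 12 months after enrollment compared to control group") and weight as changes, so both fall under this rule and their baselines enter by subtraction.

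The two questionnaires have rules of their own:

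- **SF-36.** The objective in Section 4.3 is "To compare changes in quality of life in the intervention group to the standard-of-care group". The outcome in Section 5.2 is "Quality of life at 6 months in the intervention group compared to standard of care as assessed by SF-36 questionnaire". The analysis in Section 11.1.3 is that scores are "compared between the two groups using the Mann-Whitney U-test at baseline and after 6 months".
- **SIMPAQ.** The outcome in Section 5.2 is "Changes in physical activity at 6 months compared to baseline assessed by SIMPAQ questionnaire (Endpoint: hours of physical activity"). The analysis in Section 11.1.3 is "medians of the two groups evaluated using the Mann-Whitney U-test", with no statement of which quantity the medians summarise.

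Section 11.1.3 names no covariate-adjusted model, and no effect estimate with a confidence interval, for any continuous secondary outcome. By contrast, Section 11.1.2 plans an odds ratio with a 95% CI for the primary outcome.

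In the schedules (Tables 1 and 2), HbA1c and vital signs are taken at visit 1 in both arms; Section 9.1.3.4 counts body weight among the vital signs. The SF-36 and SIMPAQ baseline forms fall at visit 2 in the intervention arm and at visit 1 in the control arm.

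**The concern.** The trial collects baseline HbA1c, weight, SF-36 and SIMPAQ in both arms but uses them either by plain subtraction or not at all. With about 28 evaluable patients per arm, precision on secondary outcomes is scarce, and adjusting for a pre-randomisation baseline is the cheapest way to gain some.

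The SF-36 plan has two further weaknesses. A between-arm significance test at baseline cannot inform on the intervention: with forms completed before allocation, any difference would be chance. On the present schedule it would mix chance with the intervention arm's reaction to a known allocation and a completed exercise session. In addition, the objective speaks of change, while the outcome definition and the test speak of level.

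For HbA1c, entry starts at 7.5% (Section 7) and the top stratum lies above 14% (Section 5.1). Section 4.3 itself asks whether the effect depends on the starting level. An arm that happens to start higher will tend to fall further, and a raw change score does not remove this.

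**Working it through.** **The plan's own figure.** The only sample-size figure is for the primary endpoint: 28 per group for 80% versus 40%, two-sided alpha 0.05, power 80%.

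- Uncorrected two-proportion formula: (1.96·√(2·0.6·0.4) + 0.842·√(0.8·0.2 + 0.4·0.6))² / 0.4² = 22.3, so 23.
- With continuity correction: (22.3/4)·(1 + √(1 + 4/(22.3·0.4)))² = 27.1, so 28. The stated figure is reproduced.
- Exact power of the two-sided Fisher test at 28 per group is 82.3%.

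This figure does not bear on the secondary outcomes; it only supplies n = 28 per arm below.

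**Inputs for the precision check.** n = 28 per arm is from the protocol. The correlation r between baseline and follow-up is not in the protocol; 0.3, 0.5 and 0.7 are assumed. Equal SDs at both times and normal data are also assumed.

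**Variance of the arm difference, with follow-up only set to 1.**

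- Change score: 2(1 − r)
- Baseline-adjusted (ANCOVA): 1 − r²
- ANCOVA relative to change score: (1 − r²) / (2(1 − r)) = (1 + r)/2

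| r | Change score | ANCOVA | ANCOVA / change score |
|---|---|---|---|
| 0.3 | 1.40 | 0.91 | 0.65 |
| 0.5 | 1.00 | 0.75 | 0.75 |
| 0.7 | 0.60 | 0.51 | 0.85 |

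The last column applies to HbA1c and weight. The ANCOVA column applies to SF-36, and to SIMPAQ if its medians are of level. If the baseline SD is k times the follow-up SD, the change-score factor becomes 1 + k² − 2rk. Its minimum, at k = r, is 1 − r². So the change score never beats adjustment, apart from the small cost of estimating the slope.

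**Detectable difference at 80% power, in SD units.** Follow-up only: (1.96 + 0.84)·√(2/28) = 0.75. For Mann-Whitney under normality, divide by √(3/π), giving 0.77. For the other two, multiply 0.75 by the square root of the variance factor:

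- Change score: 0.89 / 0.75 / 0.58 for r = 0.3 / 0.5 / 0.7
- ANCOVA: 0.71 / 0.65 / 0.53

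**Power for an illustrative 0.6 SD difference (also an assumption).**

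| r | Mann-Whitney, follow-up | Mann-Whitney, change | ANCOVA |
|---|---|---|---|
| 0.3 | 59% | 46% | 65% |
| 0.5 | 59% | 59% | 74% |
| 0.7 | 59% | 81% | 88% |

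Simulation of 4,000 trials per setting gave values 1 to 3 points lower throughout. It gave 60% / 69% / 82% for a rank-based ANCOVA, so most of the gain survives if the data are skewed.

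Below r = 0.5 a change score is less precise than follow-up alone. Replacing the 6-month SF-36 test by a plain test of change would therefore match the objective but could lose power.

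**The case against.** A reader might infer that the trial ignores baseline for its continuous secondary outcomes. The protocol does not support that: the general rule compares changes, so HbA1c and weight use their baselines. The rank-sum test is also limited to non-normal data, and how normal data are handled may properly sit in an SAP that is not shown. What stands for HbA1c and weight is that the stated approach, a raw change score, is less efficient than adjustment, and that a rank test alone gives no effect estimate.

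A reader might also infer that the SF-36 analysis is invalid or tests no defined outcome. It is neither. The 6-month test matches the outcome in Section 5.2, and under randomisation the expected arm difference is the same for level and for change. Chance baseline imbalance is already covered by the type I error and is not bias. What remains is lost efficiency and a mismatch in wording with Section 4.3.

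The SIMPAQ medians can be read as medians of change in the light of the general rule. That is ambiguity, not proven neglect of baseline.

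The size of the gain is assumed, and at r = 0.3 it is small against follow-up only: the standard error falls by about 5% (√0.91 = 0.95).

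The strongest objection concerns the questionnaires. In the intervention arm the baseline forms are completed at visit 2, after open allocation and the exercise session. Adjusting for them, or subtracting them, could introduce bias that the plain 6-month comparison avoids. Moving the forms to just before the exercise would not cure this, because Section 9.1.5 randomises before the exercise. This objection stands in full and limits the fix.

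**Conclusion.** The point holds as one of efficiency and clarity, not validity. Section 11.1.3 specifies unadjusted comparisons where baseline adjustment would be more precise. For r between 0.3 and 0.7, the variance would be 35% to 15% lower than with change scores (HbA1c, weight) and 9% to 49% lower than with a follow-up-only comparison (SF-36, possibly SIMPAQ). These sizes rest on assumed correlations, equal SDs and normal data; the direction does not depend on the exact r.

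The between-arm SF-36 test at baseline serves no purpose. Level versus change is inconsistent across Sections 4.3, 5.2 and 11.1.3 for SF-36 and unstated in Section 11.1.3 for SIMPAQ. The primary analysis is untouched, and hospitalisation counts and lengths of stay, which have no baseline, are outside the point.

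**What to change.** - **HbA1c and weight.** At each follow-up, use linear regression of the follow-up value on arm and baseline value, or a rank-based ANCOVA if the data are clearly skewed. Report the adjusted difference with its 95% CI. The baselines are already collected, so this costs only wording.
- **SF-36 at baseline.** Drop the between-arm test and describe baseline scores by arm instead.
- **Level or change.** Make Sections 4.3, 5.2 and 11.1.3 agree for SF-36 and SIMPAQ, and say in Section 11.1.3 which quantity the SIMPAQ medians summarise.
- **SF-36 and SIMPAQ from now on.** Schedule both forms before randomisation in both arms and adjust the 6-month comparison for them. This needs an amended schedule and two questionnaires at visit 1, after consent.
- **Participants under the present schedule.** Version 1.10 is dated 30.10.2023 and first enrolment was planned for 11/2018, so some forms have probably been completed at visit 2 already. For these participants keep the unadjusted 6-month comparison and state the limitation. Draw the line by enrolment period, so that both arms are treated alike.

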11.1.4 Interim Analyses

There are no interim analyses planned.

11.1.5 Safety Analysis

Descriptive analysis will be used. Please refer also to chapter 5.2

11.1.6 Deviation(s) from the Original Statistical Plan

Any deviation(s) from the original statistical plan will be described and justified in the protocol and reported to the EC.

Handling of Missing Data and Drop-outs

Results will be summarized using all available data. Multiple attempts will be made to obtain missing data. Missing data will not be imputed. Drop-outs will not be replaced.

12. QUALITY ASSURANCE AND CONTROL

Data Handling and Record Keeping/Archiving

12.1.1 Case Report Forms

A subject screening and enrollment log will be completed for all eligible or non-eligible subjects with the reasons for exclusion. For each subject enrolled a CRF must be completed and signed by the principal investigator or co-investigator. Data will be transferred from the source documents directly to the e-CRF.

All source documents, enrollment logs, p-CRFs, ICFs and other documents pertaining to the conduct of the study must be kept on file by the investigator for a minimum of 10 years after study termination. If a subject withdraws from the study, the reason must be noted in the enrollment log or p-CRF.

All participants receive an identification number (ID) and no person identifying data such as name or initials are collected in the p-CRF.

12.1.2 Specification of Source Documents

Source data (visit dates, ICFs, SAEs, AEs, concomitant medication, results of relevant examinations, laboratory values, glucose readings) will be available at the site to document the existence of the study participants. Source data will include the original documents relating to the study, as well as the medical treatment and medical history of the participant.

12.1.3 Record Keeping/Archiving

All study data must be archived for a minimum of 10 years after study termination or premature termination of the clinical trial.

Data Management

12.1.4 Data Management System

The study data collected in the p-CRF will be transferred to a web-based electronic data capture (EDC) system, named secuTrial® (version 5.3.4.6, 2018). Each EDC system of the participating centers runs on a server maintained by the appropriate IT-department of each hospital. The e-CRF is implemented by the research group in collaboration with the clinical trial unit (CTU) of the medical faculty at the University of Basel, Basel, Switzerland.

Authorized persons at the study sites are responsible for data entry into the EDC system.

12.1.5 Data Security, Access and Back-up

The EDC system is accessible via a standard browser on an web-connected device. Password protection ensures that only authorized persons can enter the system to view, add or modify data according to their permissions.

User administration and training is performed by the IT-department and CTU Basel according to predefined processes.

A regular backup of the EDC study data is performed according to the processes of the IT-department of the University Hospital Basel.

12.1.6 Analysis and Archiving

The EDC system will be locked after all data is monitored and all raised queries have been resolved.

Data is exported and transferred to the investigator by the CTU Basel according to internally defined

processes. The exported data will be archived by the investigator.

Data for analysis will be extracted from the database export and analysis will be conducted with Graph Pad Prism. Source data/documents and p-CRFs will be stored at study site for at least 10 years and be destroyed thereafter.

12.1.7 Electronic and Central Data Validation

Data is entered into the eCRF (version 5.3.4.6, 2018) and can be validated for completeness and discrepancies automatically.

An audit trail system maintains a record of initial entries and changes (reasons for changes, time and date of changes, user identification of entry and changes).

Data entered into the eCRF will be reviewed by the responsible investigator and an independent monitor will raise queries using the query management system implemented. Designated investigators have to respond to the query and confirm or correct the corresponding data. Thereafter the monitor can close the query.

Monitoring

There will be a monitoring of the study by an independent, professional, qualified study monitor from the University Hospital Basel. There will be one initiation visit and one close-out visit. The source data/documents are accessible to monitors and questions are answered during monitoring.

Audits and Inspections

Authorized representatives of the national or local health authorities and ECs will be permitted to inspect or audit the facilities, records and original data relevant to this study.

Confidentiality and Data Protection

All personal and medical information obtained for this study is confidential and disclosure to third parties other than those noted below is prohibited. Participant's data will be identified by study and subject ID number.

Upon the participant's permission, medical information will be given to his or her personal physician or other appropriate medical personnel responsible for her or his welfare.

Data generated by this study must be available for inspection upon request by representatives of the appropriate national and local health authorities, and the EC for each study site, if appropriate.

Source documents will be permitted to the study team and for purposes of monitoring, audits and inspections by local authorities and appropriate monitoring staff during and after the study. No third party will be given access to the source data. Data stored in the eCRF (secuTrial®, version 5.3.4.6, 2018) is anonymized.

Storage of Biological Material and Related Health Data

Health related data will be stored in an anonymized eCRF (secuTrial®, version 5.3.4.6, 2018). Additional samples will be taken and stored for 10 years, they will be destroyed thereafter.

13. PUBLICATION AND DISSEMINATION POLICY

The study will be published in an international peer-reviewed journal irrespective of whether its results were positive or negative.

14. FUNDING AND SUPPORT

Funding (third-party) will be applied for after approval from EC and are secured in house.

15. INSURANCE

All assessments and information material mentioned and the smart watch device in this protocol are free of charge for the subject.

The study procedures will be covered by the general liability insurance **Helvetia** of the University Hospital Basel, as will be certified by Legal Service, University Hospital Basel. A copy of the certificate will be filed in the investigator site file (ISF) and the trial master file (TMF).

17. APPENDICES

17.1 SF-36 Questionnaire

17.2 SIMPAQ Questionnaire
